## 5.4. Baseline, Post-Baseline Changes, and LOCF

Unless stated otherwise, baseline and post-baseline change values will be based on the following:

- Baseline will be based on the last non-missing value collected prior to or on the date/time of first dose of study drug.
- Post-baseline values will be those collected after the date/time of first dose of study drug.
- Change from baseline is defined as: value – baseline value.
- Percentage change from baseline is defined as:  $[(\text{value} - \text{baseline value}) / \text{baseline value}] * 100$ . Patients with baseline values of zero are excluded due to division by zero.
- Most extreme change: The maximum most extreme change will be the maximum post-baseline change value; the minimum most extreme change will be the smallest post-baseline change value. This calculation will consider all assessments collected after the first dose of study drug, scheduled or unscheduled.
- LOCF:
  - Imputation rules for assessments that include multiple components:
    - In case of missing laboratory components, lab values from the most recent unscheduled visit  $\leq 14$  days after the nominal visit will be utilized. If lab values are not available from an unscheduled visit  $\leq 14$  days after the visit, laboratory data will be carried forward from the most recent laboratory assessment  $\leq 30$  (scheduled or unscheduled) days prior to the nominal visit.
    - In case of missing non-laboratory components, no imputation will be performed.
  - In case of missing the entire score for an assessment, imputation will be based on LOCF. LOCF will only be implemented with the most recent prior visit (including unscheduled assessments). If the most recent prior visit is missing, occurred more than 30 days before (current visit date – most recent prior visit date  $> 30$ ), or is not evaluable, LOCF is not implemented. See Section 7 for further details. Additional details regarding LOCF for components for specific assessments are described in Section 7.
  - Observed values do not incorporate any imputations and are presented as collected.

## 5.5. Imputation of Partial Dates

### Adverse Events

- If the AE start date is completely missing, or if the patient was not treated, no imputation will be conducted.
- If the AE start date is missing day and month, do the following:
  - If the treatment start date is missing or the AE start year does not fall in the same year as that of the treatment start date or if the AE record contains information to

indicate that the event ended before the treatment start date (e.g. the AE end date month and year are earlier than the treatment start date or the full AE end date is known and occurs earlier than the treatment start date), then set the AE start month and day to January 1st.

- Otherwise, set the AE start date to the treatment start date.
- If only the AE start day is missing, do the following:
  - If the study treatment start date is missing or the AE start month and year does not fall in the same month and year as that of the treatment start date or if the AE contains information to indicate that the event ended before the treatment start date, then set the AE start day to the 1st day of the month of the AE start date.
  - Otherwise, set the AE start date to the treatment start date.
- AE end dates will not be imputed.

### **Prior, Concomitant, and Subsequent Medications (Excluding Corticosteroids)**

- The imputation rules for AE start dates will be used for medication start dates.
- Medication stop dates will be imputed as follows:
  - If the stop date is only missing the day, then the stop day is the last day of the month
  - If the stop date is missing both the day and month and the year matches the last study date, then the stop month and day is the earlier of the last study date and December 31
  - If the stop date is missing both the day and month and the year is earlier than the last study date, then the stop month and day is December 31
  - If the stop date is completely missing, no imputation is performed, and the medication will be classified as a concomitant medication for patients who were treated.

### **Corticosteroids**

Due to the criticality of the corticosteroid usage, handling of partial start/stop dates will be performed on a case-by-case basis as it will require medical review of the patient records. Such determinations will be made in a blinded fashion prior to database lock and approved by the Sponsor.

### **Diagnosis Date**

- If the diagnosis date is completely missing, no imputation will be conducted.
- If the month and day are completely missing but year is present, do the following:
  - Set missing month and day to July 1st
  - If July 1st of the non-missing year is after informed consent date, set month and year to January 1st
- If only the day is missing, set to the 1st of the month

## 5.6. Multiple Assessments and Visit Windows

Nominal visits (e.g. those identified by the study eCRF) will be the basis of summarization and statistical analysis unless otherwise specified. Unscheduled data may be included in summaries of most extreme, baseline, LOCF, and endpoint values; summaries of specific abnormalities any time post-baseline; and patient data listings

## 5.7. Treatment Group Display

Treatment groups will be displayed with the following columns. See the mock shells for additional details and a visual representation of the treatment group display. All overall columns will be excluded from efficacy outputs.

- Phase 1b MAD: Cohort 1 BOS 20mg
- Phase 1b MAD: Cohort 2 BOS 60mg
- Phase 1b MAD: Cohort 3 BOS 120mg
- Phase 1b MAD: Placebo
- Phase 1b MAD: Total BOS (All patients treated with BOS161721, excludes placebo)
- Phase 2 POC: BOS 120mg
- Phase 2 POC: Placebo
- Overall: Total BOS 120mg (All patients treated with BOS161721 120mg in MAD and POC)
- Overall: Total BOS (Patients treated with BOS161721 in MAD and POC, excludes placebo)
- Overall: Total Placebo (Placebo patients in MAD and POC, excludes patients treated with BOS161721)

## 5.8. Missing Data

Missing data imputation for the efficacy endpoints are discussed in the corresponding efficacy sections. AE, concomitant medication, and corticosteroid date imputations are described in Section 5.5. Missing data and other analysis conventions for noncompartmental analysis of pharmacokinetics will follow standard imputation methods, as described in a separate Clinical Pharmacology SAP. Otherwise, missing data will not be imputed.

# 6. STUDY PATIENT DATA

## 6.1. Analysis Populations/Sets

**FAS:** Defined as all patients who receive at least one dose (partial or complete) of study treatment and have at least one evaluable post-baseline efficacy evaluation (BILAG, PGA,

Sponsor: Boston Pharmaceuticals, Inc.  
Protocol Number: BOS161721-02  
SAP Version and Date: Version 4.0, 23Apr2021

SLEDAI-2K, CLASI, ACR-28, SLICC/ACR, **CCI** [REDACTED], or **CCI** [REDACTED]). FAS analyses will be conducted on the basis of the assigned (randomized) treatment. The FAS will be used as the basis for the primary efficacy analysis.

**Safety Analysis Set (SS):** Defined as all patients who receive at least one dose (partial or complete) of study treatment and have at least one evaluable post-baseline safety evaluation (adverse events, concomitant medications, vital signs, physical examination, ECG, or laboratory assessment). Safety analyses will be conducted on the basis of actual treatment received as reported on the eCRF. The SS will be the basis of all safety reporting.

**Per Protocol Set (PP):** Defined as all patients from the FAS except those with major deviations to the protocol deemed to impact the analysis of the primary endpoint. These deviations will be identified based on blinded data review prior to study unblinding. Patients with more than one missed dose and patients with both Day 180 and Day 210 efficacy assessments (BILAG, SLEDAI-2K, or PGA) missing will be excluded from the PP. PP analyses will be conducted on the basis of the assigned (randomized) treatment. Additional information on inclusion into this population can be found in Section 6.3.

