### 3.3. Sample Size Considerations

Sample size in the Phase 1b part of the study is based on operational consideration.

The sample size in the Phase 2 POC study is based on the primary endpoint, SRI-4 Response at Day 210. Based on efficacy data from a recently completed study with Ustekinumabiii, where the primary endpoint was also SRI-4, the sample size in the phase 2 part of the BOS161721-02 study is set at 96 evaluable patients. In the Ustekinumab study of 102 patients, a statistically significant difference in SRI-4 response was shown in favor of Ustekinumab (62% of Ustekinumab treated patients achieved SRI-4 response vs. 33% in patients receiving placebo). The Ustekinumab phase 2 study is an appropriate comparator to BOS161721-02 because both studies share the same primary endpoint of SRI-4 response and BOS161721 and Ustekinumab have overlapping mechanisms of action (T follicular helper and Th17 cell biology).

Sponsor: Boston Pharmaceuticals, Inc.  
Protocol Number: BOS161721-02  
SAP Version and Date: Version 4.0, 23Apr2021

Approximately 110 additional patients will be randomized in a 2:1 ratio to BOS161721 versus placebo to achieve approximately 96 evaluable patients in the FAS of the phase 2 portion. This assumes 14 patients will discontinue prior to having received treatment or having completed a post-baseline efficacy measure. Enrollment and randomization will be monitored in a blinded fashion and may be increased if needed to ensure at least 96 evaluable patients are randomized into the FAS (see Section 6.1).

A total of 96 evaluable patients randomized provides 80% power to detect a treatment difference of 29% in SRI-4 response rates at Day 210, based on a targeted 2-sided significance level of 10% and using a 2-sided Pearson's chi-squared test. This assumes a response rate of 62% for BOS161721 and 33% for placebo.

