#### **Early Treatment Withdrawals/Discontinuations:**

For early treatment withdrawal/discontinuation prior to study day 159 (180 days – 21 day treatment window), patient will be considered a non-responder after the date of early treatment withdrawal/discontinuation assuming the patient was not considered a medication failure prior to or on the date of early withdrawal/discontinuation for the primary efficacy analysis.

For early treatment withdrawal/discontinuation on or after study day 159 (180 days – 21 days) such that patient has data for nominal visit Day 180 but not for nominal visit Day 210, Day 180 data will be carried forward to Day 210 for assessment of SRI-4 response.

For early treatment withdrawal/discontinuation on or after study day 159 (180 days – 21 days) such that patient does not have data for nominal visit Day 180 and Day 210, the patient will be considered a non-responder on Day 210.

For early treatment withdrawal/discontinuation on Day 210 such that patient has data for nominal visit Day 210, the Day 210 data will be used for assessment of SRI-4 response.

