**Table 2**

| Analysis   | Analysis Population | Criteria   |
|--|---------------------|--|
| Primary Analysis

LOCF for missing data,
Medication
Failures=Non-Responder | FAS                 | 
The primary analysis of the primary efficacy endpoint will be performed based on LOCF methods for missing data.
 
 
(1) Medication failures are considered non-responders on and after the date of medication failure
 
(2) Early withdrawals/discontinuations prior to study day 159 will be considered non-responders after the date of early withdrawal/discontinuation
 
 |

|  |     |  |
|--|-----|--|
|  |     | 
 
a. If patient is a medication failure prior to withdrawal/discontinuation, patient will be considered a non-responder on and after the date of medication failure.
 
b. In case of early withdrawal/discontinuation after study day 159 but before Day 210 such that patient has Day 180 data but is lacking Day 210 data in a patient without medication failure, the Day 180 data will be carried forward to Day 210.
 
 
(3) Patients with missing Day 180 and Day 210 data without prior medication failure and without early withdrawal/discontinuation prior to study day 159 are considered not evaluable and are excluded from analysis
  |

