### 8.3. Immunogenicity

Immunogenicity data as collected on the eCRF will be provided in by-patient data listings including neutralizing antibodies (NAb) and ADA for all relevant timepoints.

All serum ADA samples that are confirmed positive in the ADA assay will be analyzed for the presence of NAb.

The proportion of patients with positive or negative ADA will be summarized by study phase, treatment group, and overall, at baseline (pre-dose), and post-baseline in the FAS. The frequency and percentage of patients with transient positive and persistent positive ADA will also be included in the summary. If warranted based on data, treatment-emergent transient positive and treatment-emergent persistent positive ADA will be summarized. The frequency and percentage of patients with confirmed positive, treatment-emergent confirmed positive, and negative ADA at each post-baseline timepoint will also be summarized. ADA designations and denominators are defined in table 7.

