|                                 | Treatment-Emergent | 
Scenario 1:
 
(1) Negative ADA at baseline
 
(2) Confirmed positive ADA at the post-baseline timepoint
 
Scenario 2:
 
(1) Confirmed positive ADA at baseline
  |   |

|         |          |  |  |
|---------|----------|--|--|
|         |          | (2) Confirmed positive ADA at the post-baseline timepoint and the titer at the of the confirmed positive ADA is $\geq 4$ times greater than the baseline titer |  |
|         | Negative | Negative ADA at the post-baseline timepoint  |  |
| Overall | Positive | A patient with positive baseline (pre-dose) ADA or positive post-baseline ADA  | Number of patients with a baseline or post-baseline ADA assessment |
|         | Negative | A patient with negative baseline (pre-dose) ADA and negative post-baseline ADA at all time points  |  |

The frequency and percentages of positive and negative neutralizing antibodies will be summarized in the FAS overall and at each relevant post-baseline timepoint (i.e., Day 15, Day 30, Day 60, Day 90, Day 180, Day 270). The denominators will be the number of patients with non-missing NAb data overall and at each timepoint, respectively.

The adverse event overview table from section 10.1 will be repeated by post-baseline positive and negative ADA as defined in table 7 in the safety analysis set. Additional adverse event analyses may be performed by post-baseline transient positive and persistent positive.

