## 10. SAFETY

All safety analysis reporting will be based on the Safety Analysis Set. Unless otherwise noted, all safety analyses will be presented overall, by study phase, and treatment group.

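### The FAS drops dosed patients with no post-baseline efficacy evaluation, although the primary analysis counts treatment stops before study day 159 as non-response; antibody summaries also use the FAS rather than the safety set

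*SAP*

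**What the plan says.** Section 6.1 requires a FAS patient to "receive at least one dose (partial or complete) of study treatment and have at least one evaluable post-baseline efficacy evaluation". Six instruments are named there (BILAG, PGA, SLEDAI-2K, CLASI, ACR-28, SLICC/ACR) and two are redacted; one evaluable result on any of them is enough. Patients are analysed as randomised, and "The FAS will be used as the basis for the primary efficacy analysis".

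Section 7.1.1, on early treatment withdrawal before study day 159, says the "patient will be considered a non-responder after the date of early treatment withdrawal/discontinuation". The primary-analysis row of Table 2 repeats it: "Early withdrawals/discontinuations prior to study day 159 will be considered non-responders after the date of early withdrawal/discontinuation".

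Section 3.3 plans about 110 randomised patients to obtain 96 in the FAS: "This assumes 14 patients will discontinue prior to having received treatment or having completed a post-baseline efficacy measure". Enrolment may be raised to reach 96.

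On antibodies, Sections 2.1 and 2.2 list ADAs under safety endpoints. Section 6.1 makes the Safety Analysis Set (SS), grouped by actual treatment, the basis of safety reporting, and Section 10 states that "All safety analysis reporting will be based on the Safety Analysis Set". Section 8.3, however, summarises ADA by study phase, "treatment group, and overall, at baseline (pre-dose), and post-baseline in the FAS", and does the same for NAb, while its adverse-event overview by ADA status uses the SS.

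**The concern.** The analysis set is applied before the response rule. The plan has decided that stopping early is a failure, but it exempts those who stop so early that they contribute no efficacy evaluation. Two dosed patients who both stop before day 159 are treated differently: one with a single CLASI or PGA result is a non-responder, and one with no result is absent from numerator and denominator. Inclusion then depends on something that happens after randomisation and that treatment can influence, such as intolerance, a reaction or worsening lupus. If this loss differs between arms, the comparison is no longer between the groups as randomised and dosed. Enrolling more patients restores the count of 96 but not the balance.

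The antibody point is of the same kind but smaller. One ADA classification is reported in two sets and on two treatment bases within one section, and a patient with an antibody sample but no efficacy evaluation is left out of the ADA incidence.

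**Working it through.** **1. The plan's own figure.** Inputs from Section 3.3: 62% vs 33%, 2:1 allocation, two-sided alpha 0.10, power 80%. The two-proportion sample-size formula with continuity correction gives 32 placebo + 64 active = 96, which matches. Without the correction, which is the Pearson test as named, 81 would do, and 96 patients give 86.2% power. That gap does not affect this point.

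**2. Who is lost.** Section 3.3 allows for 110 − 96 = 14 losses (12.7%), made up of never-dosed patients and dosed patients without an efficacy measure. The SAP does not give the split. Let k be the dosed part; k lies between 0 and 14. Never-dosed patients stay out under either definition.

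**3. Does another analysis restore them?** The primary analysis and all four sensitivity analyses in Table 2 name the FAS. The per-protocol set is a subset of the FAS. Further missing-data analyses are optional and name no wider set. So none does.

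**4. Effect on the difference.** Assume 110 at 2:1 is 73 active and 37 placebo, and that the FAS shows exactly the planned 62% and 33%. If a active and b placebo patients are left out and are then counted as non-responders:

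- active rate = 0.62 × (73 − a) / 73
- placebo rate = 0.33 × (37 − b) / 37
- z = difference / √[p(1 − p)(1/n₁ + 1/n₂)], with p the pooled rate

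| Left out (a:b) | Active | Placebo | Difference | z in FAS | z with them counted |
|---|---|---|---|---|---|
| 9:5 (about 2:1) | 39.68/73 = 54.4% | 10.56/37 = 28.5% | 25.8 points | 2.68 | 2.57 |
| 7:0 | 40.92/73 = 56.1% | 33.0% | 23.1 points | 2.83 | 2.29 |
| 12:2 | 37.82/73 = 51.8% | 11.55/37 = 31.2% | 20.6 points | 2.74 | 2.05 |
| 14:0 | 36.58/73 = 50.1% | 33.0% | 17.1 points | 2.77 | 1.71 |
| 0:14 | 62.0% | 7.59/37 = 20.5% | 41.5 points | 2.44 | 4.12 |

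The two-sided 10% cut-off is 1.645. With an exact 2:1 loss of all 14, both rates shrink by 96/110, the difference is 25.3 points, and uncorrected Pearson power is 82.2% against 86.2%.

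**5. Can the decision change?** Near the limit, yes. Suppose the FAS gives 34/64 vs 11/32, p = 0.083, which the SAP would call superior. Adding non-responders gives:

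- 9 active and 5 placebo: 34/73 vs 11/37, p = 0.09 (unchanged)
- 10 and 4: 34/74 vs 11/36, p = 0.123 (changed)
- 14 and 0: 34/78 vs 11/32, p = 0.37 (changed)

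**6. Worst case for error.** If the true rate among dosed patients were 28.8% in both arms, and 14 of 73 active but no placebo patients were left out, the exact two-sided error would be 0.17, with 0.16 favouring active against a nominal 0.05.

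**7. Denominators.** The SRI-4 disposition summary in Section 7.1.1 and the by-visit analysis in Section 7.2.1 define their denominators as patients with PGA, SLEDAI-2K and BILAG data at the visit. Read literally, these also leave out patients who are non-responders by rule. Changing the FAS alone would not bring the lost patients back there.

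**8. Antibodies.** The NAb summary is "at each relevant post-baseline timepoint (i.e., Day 15, Day 30" and later visits. The Table 7 denominators already require an antibody sample. Moving from FAS to SS therefore changes the result only for patients with a sample but no efficacy evaluation, or for patients who received a treatment other than the one assigned.

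**The case against.** A reader might infer that anyone who stops before the Day 30 visit is deleted. The SAP does not support that. One evaluable result on any listed instrument keeps a patient in the FAS. Section 7.1.1 explains that the Day 180 record doubles as the end-of-treatment record and needs a day-159 limit, so end-of-treatment assessments before that day are foreseen. Appendix 13.1 points to premature-discontinuation assessments in the protocol. A patient who stops on day 20 and is assessed at such a visit is in the FAS and is a non-responder. The Day 30 start of the SRI listing does not show when each instrument is first collected; that schedule is in the protocol. This part of the objection stands, and the point is limited accordingly.

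It also stands that 14 is a ceiling, that nothing in the SAP suggests a lopsided loss, and that a balanced loss costs little: power stays above the planned 80%. At the planned rates even 14:0 leaves z above the cut-off.

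Sections 6.2 and 7.1.1 give some visibility: set membership and discontinuation reasons by arm, and a listing of those excluded from the primary analysis. That would show an imbalance, but it would not supply an estimate that includes the patients.

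On antibodies, Section 8 calls immunogenicity secondary or exploratory, and all results are listed by patient, so no positive result is hidden. The conflict with Sections 2.1, 2.2, 6.1 and 10 remains.

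**Conclusion.** The point holds in a limited form. Sections 6.1 and 7.1.1 treat the earliest dosed stoppers inconsistently, inclusion depends on a post-randomisation event, and no specified analysis corrects for it. The size is not known. It rests on k (0 to 14), on the split between arms, and on the planned rates holding in the FAS. At the upper bound the 29-point difference becomes about 26 with a loss near 2:1, about 17 if all are on active (z from 2.77 to 1.71), and about 41 if all are on placebo. A reader might conclude that the primary result is biased in favour of the drug; the SAP does not support a direction, since that depends on which arm loses more. It should be corrected before unblinding, because choosing the set afterwards would not be credible.

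The antibody point is a minor inconsistency of analysis set and treatment grouping, and few patients are likely to be affected.

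**What to change.** 1. Section 6.1: define the FAS as all randomised patients who received at least one dose, analysed as randomised. Reword the Section 3.3 sentence on the 14 losses to match.
2. Section 7.1.1 and Table 2: state that a dosed patient who stops treatment before study day 159 without any efficacy evaluation is a non-responder under the existing rule.
3. Sections 7.1.1 (disposition summary) and 7.2.1: align the denominators with that rule, so that patients who are non-responders by rule are counted even without PGA, SLEDAI-2K and BILAG data at the visit.
4. Keep the current FAS definition as a named sensitivity set.
5. Section 8.3: summarise ADA and NAb in the SS by actual treatment, keeping the Table 7 sample requirements.

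The cost is SAP wording, a derived flag and revised denominators in the affected tables; no new data are needed. The downside is that response rates may look slightly lower.
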